5.1.3 Administration of Test Drug

The 1st dose, or Day 1 dose, of the assigned study treatment (test drug) will be administered in a hospital setting immediately after the subject is enrolled.

The second dose of the assigned study treatment (test drug) will be given on Day 4, or 3 days after the 1st dose.

A total of no more than two doses of study treatment (test drug) will be given.

5.1.4 Packaging and Labeling of Test Drug

The sponsor will supply the sterile ready to use DUR-928 for Injection:

- PPD/CCI [REDACTED]

The concentration of the DUR-928 Injection product to be used in this study is PPD/CCI [REDACTED]

The sponsor will supply 5 mL vials of Sterile Water for Injection, USP (placebo).

Each vial is labeled with product name, lot number, and quantity.

5.1.5 Storage of Test Drug

Both DUR-928 Injection and Sterile Water for Injection, USP (placebo) should be stored at PPD/CCI [REDACTED]

5.1.6 Preparation of Test Drug

The assigned study treatment (DUR-928 Injection or placebo) will be diluted into a PPD/CCI [REDACTED]

More details will be provided in the Pharmacy Manual for this study.

5.1.7 Drug Accountability

All materials supplied are for use only in this clinical study and should not be used for any other purpose.

The Investigator is responsible for investigational product accountability, reconciliation, and record maintenance at the investigational site. In accordance with all applicable regulatory requirements, the Investigator or designated site staff (e.g. unblinded pharmacist) must maintain investigational product accountability records throughout the course of the study. This person will document the amount of investigational product received from PPD/CCI [REDACTED] the amount administered to subjects, and the amount of investigational product remaining.

A Drug Dispensing Log must be kept current and will contain the following information:

- Study identification of the subject to whom the drug was dispensed;
- Date(s), study treatment, and quantity of the drug dispensed to each subject.

The inventory must be available for inspection by the unblinded study monitor during the study. Drug supplies will either be returned by the Investigator or designee to DURECT or, if requested in writing by the Sponsor, unused drug supplies may be destroyed by the clinical study unit according to local standard operating procedures (SOPs). Records shall be maintained by the Investigator of any such alternate disposal of the test drug. These records must show the identification and quantity of each unit disposed of, the method of destruction (taking into account the requirements of local law), and the person who disposed of the test substance. Documentation of the disposition of all IP will be provided to DURECT. If the clinical study unit is unable to dispose of the investigational product, unused drug will be returned to DURECT.

5.2 Trial Visits and Study Procedures

Refer to [Table 1](#) for an overview of the schedule of events by visit.

5.2.1 Screening (Day -4 to Day-1)

The screening visit will be performed up to 4 days prior to the day of dosing. After obtaining informed consent, subjects will be assigned a subject number and screening procedures will be performed. For the subject number, subjects will be numbered consecutively within each site in order of their consent into the trial. Only their assigned subject number and date of birth will identify subjects to the Sponsor in order to maintain anonymity.

Screening procedures include completion of:

- Informed Consent
- Demographic information
- Medical and surgical history
- Review of inclusion / exclusion criteria
- Physical examination (including height and weight)
- Vital signs (BP, HR, respiratory rate, oxygen saturation, and temperature)
- Safety laboratory tests (chemistry, hematology, urinalysis, coagulation)
- Urine or serum pregnancy test (females of childbearing potential) performed locally
- 12-lead ECG
- Record prior and concomitant medications (taken within 30 days of screening)

5.2.2 Day 1 (In-hospital, Study Treatment)

The following procedures will be performed pre-dose unless otherwise noted:

- Review of inclusion / exclusion criteria to confirm eligibility
- Vital signs (BP, HR, respiratory rate, oxygen saturation, and temperature) pre-dose
- Physical exam (including weight) when feasible
- PPD/CCI 
- Safety labs (chemistry, hematology, urinalysis, coagulation) at pre-dose
 - NOTE: If a subject is screened and dosed on the same day, only the safety labs for Screening should be collected. An additional collection for Day 1 Pre-dose safety labs does **not** need to be performed.
- 12-lead ECG (post-dose completion/end of infusion)
- Adverse events and concomitant medications
- Biomarker samples collection (blood) at pre-dose when feasible
- Randomization

- Study Drug Dosing

5.2.3 Day 2

- Vital signs (BP, HR, respiratory rate, oxygen saturation, and temperature)
- Physical exam (including weight) when feasible
- PPD/CCI [REDACTED]
- Safety labs (chemistry, hematology, urinalysis, coagulation)
- Biomarker samples collection (blood) when feasible
- 12-lead ECG (when feasible)
- Adverse events and Concomitant medications

5.2.4 Day 3

- Vital signs (BP, HR, respiratory rate, oxygen saturation, and temperature)
- Physical exam (including weight) when feasible
- Safety labs (chemistry, hematology, urinalysis, coagulation)
- Biomarker samples collection (blood) when feasible
- 12-lead ECG (when feasible)
- Adverse events and concomitant medications

5.2.5 Day 4

- Vital signs (BP, HR, respiratory rate, oxygen saturation, and temperature) pre-dose
- Physical exam (including weight) when feasible
- Safety Labs (chemistry, hematology, urinalysis, coagulation) pre-dose
- 12-lead ECG (post-dose completion/end of infusion)
- Adverse events and Concomitant medications
- Biomarker samples collection (blood) at pre-dose when feasible
- PPD/CCI [REDACTED]
- Study drug dosing (Dose 2 of assigned study drug)

5.2.6 Day 5 and Day 6

Subjects will not be kept in the hospital longer than is medically required. If subjects remain hospitalized on Day 5 and Day 6, the following procedures will be performed and, *regardless*

of hospitalization, occurrence of AEs, and intake of concomitant medications will be assessed (in person or via phone contact):

- Vital signs (BP, HR, respiratory rate, oxygen saturation, and temperature)
- Physical exam (including weight) when feasible
- Safety labs (chemistry, hematology, urinalysis, coagulation)
- Biomarker samples collection (blood) when feasible
- PPD/CCI [REDACTED]
- 12-lead ECG (when feasible)
- Adverse events and Concomitant medications

5.2.7 Day 7 (± 1 day)

The following procedures will be performed via clinic visit on Day 7, or in the hospital if the subject has not been discharged. Day 7 and Day 6 visits should not occur on the same day. If a subject is going to be discharged from the hospital on Day 6, then the Day 6 visit should **not** be completed and the Day 7 visit should be completed per visit window.

- Vital signs (BP, HR, respiratory rate, oxygen saturation, and temperature)
- Physical exam (including weight) when feasible
- Safety labs (chemistry, hematology, urinalysis, coagulation)
- Biomarker samples collection (blood) when feasible
- 12-lead ECG
- Adverse events and Concomitant medications

5.2.8 Days 8-14 (± 3 days)

Subjects will not be kept in the hospital longer than is medically required. If subjects remain hospitalized on Day 8-14, the following procedures will be performed, and, *regardless of hospitalization, occurrence of AEs, and intake of concomitant medications will be assessed (in person or via phone contact)*. A clinic visit will be performed on Day 14.

- Vital signs (BP, HR, respiratory rate, temperature)
- Physical exam (including weight) when feasible
- Safety labs (chemistry, hematology, urinalysis, coagulation)
- Biomarker samples collection (blood) when feasible
- Adverse events and Concomitant medications

5.2.9 Day 28 (± 3 day) Trial Completion / Early Termination

The following procedures will be performed via clinic visit on Day 28:

- Physical Exam (including weight) when feasible

- Vital signs (BP, HR, respiratory rate, temperature)
- Urine or serum pregnancy test (females of childbearing potential) performed locally
- Safety labs (chemistry, hematology, urinalysis, coagulation)
- Biomarker samples collection (blood) when feasible
- 12-lead ECG
- Adverse events and Concomitant medications

5.2.10 Day 60 (±3 day) End of Study Follow up

The following procedures will be performed by phone:

- Adverse events and Concomitant medications

5.3 Concomitant Medication(s)

Any required treatment deemed necessary for treatment of the subject will be under the treating physician's discretion and given as medically required. All concomitant medications will be recorded on the appropriate eCRF.

6.0 ASSESSMENT OF EFFICACY

6.1 Efficacy Assessments

Primary:

- Evaluate safety in subjects treated with DUR-928 as evidenced by treatment-emergent serious adverse events (TESAEs), including
 1. Respiratory failure events
 2. Liver failure events
 3. Renal failure events
 4. Heart failure events
 5. Secondary infection (regardless viral or non-viral)
- Evaluate efficacy of DUR-928 in treatment of acute organ failure, especially acute liver or kidney injury, in subjects infected with SARS-CoV-2. The primary efficacy endpoint is the composite of being alive and free of acute organ failure at Day 28. This is specifically defined as being:
 - Alive at Day 28
 - Free of mechanical ventilation at Day 28
 - Free of acute liver failure (i.e., free of the simultaneous presence of: jaundice, coagulopathy, ascites, and hepatic encephalopathy) at Day 28
 - Free of renal replacement therapy at Day 28

Secondary:

- Alive at Days 28 and 60
- Alive, out of ICU, at Day 28
- Alive, out of hospital, at Days 28 and 60

PPD/CCI [Redacted]

[Redacted]

[Redacted]

[Redacted]

[Redacted]

[Redacted]

[Redacted]

[Redacted]

[Redacted]

[Redacted]

[Redacted]

[Redacted]

[Redacted]

[Redacted]

[Redacted]

[Redacted]

[Redacted]

[Redacted]

[Redacted]

[Redacted]

[Redacted]

[Redacted]

[Redacted]

[Redacted]

[Redacted]

[Redacted]

[Redacted]

[Redacted]

6.1 [REDACTED]

6.2 [REDACTED]

6.3 [REDACTED]

6.4 [REDACTED]

6.5 [REDACTED]

6.6 [REDACTED]

6.2 Method and Timing of Assessments

Safety Labs will be collected at:

- Screening
- Pre-dose on Day 1
- Pre-dose on Day 4
- Daily during hospitalization, Day 7,14, and Day 28

See Table 1 for further details and timing of study procedures.

7.0 ASSESSMENT OF SAFETY

7.1 Safety Assessments

Each subject will be followed up for 60 days for safety assessment. Day 60 assessment will be conducted by phone interview.

Safety will be determined based on clinical and laboratory monitoring.

Clinical: Vital signs, and physical examination (when feasible), should be recorded and examined daily while in hospital or during scheduled clinical visits with specific attention to pulmonary abnormalities, worsening in liver and kidney functions. Other decompensation events, including ascites and hepatic encephalopathy, will be monitored clinically.

Laboratory: Biochemical parameters that are monitored daily while in hospital or during scheduled clinical visits include liver biochemistry (daily assessment of PT in subjects with coagulopathy may be affected), hematology, creatinine, urinalysis, and serum chemistries. MELD Na, Child’s Pugh Turcotte, and CLIF scores in subjects with acute on chronic liver disease will also be monitored when feasible and available.

Viral Test: Viral RNA will be monitored for as long as it continues to be shed in nasopharyngeal oropharyngeal and stool samples of each subject by the standard quantitative RT-PCR.

Data Monitoring Committee (DMC): The mission of the DMC will be to safeguard patient interests and to enhance trial integrity. To address this mission, DMC will meet on a regular basis to review unblinded data on efficacy, safety and quality of trial conduct.

Monitoring Process and Individual Subject Stopping Rule: During the trial, individual subjects will be evaluated by the site PI if any of the following SAE occurs. The PI and medical monitor, based on the nature and severity of the event(s), will determine if the event(s) warrants the early termination of the study therapy in the best interest of the subject.

The DMC may also provide recommendations as needed.

1. Appearance of DILI:
 - a. If baseline measurements (BLM) were $<2x$ ULN, discontinue if ALT or AST increases to $>5x$ BLM;
 - b. If $BLM \geq 2x$ ULN but $<5x$ ULN, discontinue if ALT or AST increases to $>3x$ BLM;
 - c. If $BLM \geq 5x$ ULN, discontinue if ALT or AST increases to $>2x$ BLM;
 - d. Discontinue if ALT or AST increase $> 2x$ BLM AND the increase is accompanied by a concomitant increase in TBL to $>2x$ BLM OR the INR concomitantly increases by >0.2 in absence of COVID-19 coagulopathy;
 - e. In any subjects with signs and symptoms of fatigue, nausea, vomiting, right upper quadrant pain or tenderness, fever, rash, and/or eosinophilia ($> 5\%$ or $> 500/\mu L$)
2. Worsening of COVID-19 severity
3. SAE events associated with cardiac, kidney, liver, or secondary infection.

The DMC also will be contacted on an as needed basis by the medical monitor to review available data, unblinded by intervention group, providing insights about whether any unexpected SAE (or SUSAR) could be due to study drug rather than the underlying COVID-19 disease and to provide advice regarding study conduct.

In accordance with the Charter, the DMC review of unblinded data will occur promptly to address situations listed in Section 11.5, for example,

- PPD/CCI [REDACTED]
- more than 2 subjects have an AE grade 3 or above on the CTCAE scale that is determined to be possibly or probably attributable to study drug as per the medical monitor;
- more than 3 deaths, and the overall percentage of study patients with deaths within 60 days exceeds 10%.

Based on data review, DMC could recommend termination of the trial, pausing of randomization, discontinuation of treatment, or continuation of the trial.

Refer to Section 11.5.

The following parameters will be recorded daily for the safety evaluation:

- Serious adverse events

- Standard 12-lead ECG
- Safety Laboratory Tests (clinical chemistry, hematology, coagulation, and urinalysis)
- Vital Signs
- Physical examination (when feasible)

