9.5 Planned Interim Analyses

Not applicable.

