11.5 Data Monitoring Committee (DMC)

An independent, external DMC that includes a hepatologist, a nephrologist and an ICU specialist will convene prior to study start, once the PPD/CCI [REDACTED] enrolled and their PK data available, once PPD/CCI [REDACTED] have been treated and followed for PPD/CCI [REDACTED] to monitor the study for safety events including SAEs, death, premature discontinuation of treatment for SAEs, or any treatment-emergent laboratory abnormalities.

DMC will evaluate (based on an unblinded review of safety data) if there is:

1. PK data and safety review of the PPD/CCI [REDACTED];

2. a >20% of subjects in the DUR-928 group than in the placebo group with treatment-emergent, treatment-related serious adverse event(s) of a specific type;
3. more than 3 deaths, and the overall percentage of study patients with deaths within 60 days exceeds 10%.
4. more than 2 subjects have an AE grade 3 or above on the CTCAE scale that is determined to be possibly or probably attributable to study drug as per the medical monitor.

The DMC also will be contacted on an as needed basis by the medical monitor to review available data, unblinded by intervention group, providing additional insights about whether any unexpected SAE (or SUSAR) to an individual subject could be due to study drug rather than the underlying COVID-19 disease and to provide advice regarding study conduct. The PI and medical monitor, based on the nature and severity of the event(s) under the Individual Subject Stopping Rule as listed below, will determine if such event(s) warrant the early termination of the study therapy in the best interest of the subject. The DMC may also provide recommendations as needed.

Individual Subject Stopping Rule:

1. Appearance of DILI:
 - a) If baseline measurements (BLM) were <2x ULN, discontinue if ALT or AST increases to >5x BLM;
 - b) If BLM \geq 2x ULN but <5x ULN, discontinue if ALT or AST increases to >3x BLM;
 - c) If BLM \geq 5x ULN, discontinue if ALT or AST increases to >2x BLM;
 - d) Discontinue if ALT or AST increase > 2x BLM AND the increase is accompanied by a concomitant increase in TBL to >2x BLM OR the INR concomitantly increases by >0.2 in absence of COVID-19 coagulopathy;
 - e) In any subjects with signs and symptoms of fatigue, nausea, vomiting, right upper quadrant pain or tenderness, fever, rash, and/or eosinophilia (> 5% or > 500/ μ L)
2. Worsening of COVID-19 severity

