3. SAE events associated with cardiac, kidney, liver, or secondary infection.

The DMC will provide recommendations to DURECT on whether the nature, frequency, and severity of adverse effects associated with study treatment warrant the early termination of the study in the best interest of the participants, whether the study should continue as planned, or the study should continue with modifications. The DMC may also provide recommendations as needed regarding study design.

The DMC's specific activities will be defined by a mutually agreed charter, which will define the DMC's membership, conduct and meeting schedule. While the DMC will be asked to

advise the sponsor regarding future conduct of the study, including possible early study termination, DURECT retains final decision-making authority on all aspects of the trial.

Based on data review, DMC could recommend termination of the trial, pausing of randomization, discontinuation of treatment, or continuation of the trial.

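### Does the DMC's regular view of unblinded efficacy put the final test at risk when Section 9.5 plans no interim analysis?

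*Combined protocol and SAP*

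**What the plan says.** - **Synopsis and Section 7.1:** the same sentence appears in both: "DMC will meet on a regular basis to review unblinded data on efficacy, safety and quality of trial conduct". After a list of situations calling for prompt DMC review, both add: "Based on data review, DMC could recommend termination of the trial, pausing of randomization, discontinuation of treatment, or continuation of the trial".
- **Section 9.5, Planned Interim Analyses:** the whole entry is "Not applicable".
- **Section 11.5:** the DMC convenes to monitor safety events, with PK data at one review. The list of things it assesses opens with "DMC will evaluate (based on an unblinded review of safety data) if there is". The medical monitor may also ask it, as needed, to "review available data, unblinded by intervention group", in order to judge whether an unexpected serious event is due to study drug.
- **Section 11.5, recommendations:** the DMC advises whether the "nature, frequency, and severity of adverse effects associated with study treatment warrant the early termination of the study". It also says: "The DMC may also provide recommendations as needed regarding study design". The sponsor decides: "DURECT retains final decision-making authority on all aspects of the trial".
- **Sections 9.1, 9.2 and 9.4:** efficacy analyses are called exploratory and the trial a screening evaluation. Particular attention goes to the pre-specified primary endpoint, compared by a Pearson chi-square test in 80 subjects randomized 3:1.

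Section 11.5 leaves the DMC's conduct and meeting schedule to a charter that is not among the documents. Text is redacted in 9.1, in 9.2 directly after the chi-square sentence, in the first DMC trigger and in the DMC meeting times.

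**The concern.** Three places describe the DMC's access to efficacy differently: regular unblinded review in 7.1 and the synopsis, a safety and PK remit in 11.5, and no interim analysis in 9.5. The DMC may recommend termination and may advise on design, and no legible sentence says that favourable efficacy cannot prompt either. A reader could infer that the trial might be stopped or reshaped on a good early result, with no boundary and no adjustment of the final test.

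That would matter. Repeated unadjusted looks with stopping for benefit raise the chance of a false claim of benefit, and the primary comparison is the one efficacy result to which the protocol promises particular attention.

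**Working it through.** **1. The plan's own figure.** 80 subjects at 3:1 gives 80 × 3/4 = 60 on DUR-928 and 80 × 1/4 = 20 on placebo. The power calculation behind 80 cannot be reproduced, because alpha, power and responder rates are not legible in 9.2.

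**2. Could efficacy stop or change the trial under the text?**

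| Text | Where it sits | Tied to favourable efficacy? |
|---|---|---|
| Regular review of efficacy, safety and conduct | Safety text of the synopsis and 7.1 | No; gives access, no decision rule |
| Termination after data review | Synopsis and 7.1: closes the list of prompt-review situations; 11.5: follows the safety remit | No; every legible situation is a safety one |
| Review of available unblinded data | 7.1 and 11.5, on request | No; tied to unexpected serious events |
| Early termination of the study | 11.5 | No; the ground is adverse effects |
| Advice on study design | 11.5 | Not tied to any trigger |
| Interim analyses | 9.5 | None planned |

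Only the design-advice sentence is open-ended, and nothing links it to efficacy. The 9.5 entry agrees with the rest if the DMC sees efficacy for benefit-risk only, which is ordinary practice.

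**3. What would be at stake if the text did allow stopping for benefit.** From the documents: 60 versus 20 and the Pearson chi-square. Assumed: two-sided 0.05 at every look, the number and timing of looks, stopping at the first favourable crossing, 3:1 within every 4 subjects, no continuity correction, and the same true responder rate in both arms.

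With x responders of n on DUR-928, y of m on placebo, and p = (x + y)/(n + m), the statistic at each look is

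z = (x/n − y/m) / √[p(1 − p)(1/n + 1/m)].

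A false claim of benefit is z > 1.96 at any look. Results from 400,000 simulated trials per cell:

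| Looks (total subjects) | Rate 0.5 | 0.6 | 0.7 | 0.8 |
|---|---|---|---|---|
| 80 only | 2.40% | 2.75% | 2.85% | 2.90% |
| 40, 80 | 4.26% | 4.59% | 4.70% | 4.73% |
| 28, 52, 80 | 5.73% | 6.17% | 6.44% | 7.02% |
| 20, 40, 60, 80 | 6.54% | 7.16% | 7.56% | 7.78% |

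A large-sample check with equally spaced looks (2,000,000 replicates) gives 2.5%, 4.2%, 5.4% and 6.3% for 1, 2, 3 and 4 looks.

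**4. Which row is the plan?** The first. The other rows need a rule that stops for benefit, and step 2 finds none. Seeing efficacy without acting on it leaves the final test as it was.

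**5. How far the other rows depend on assumptions.** A first look at 20 subjects has 5 on placebo, so the expected number of placebo non-responders is 5 × 0.2 = 1.0 to 5 × 0.5 = 2.5. The chi-square approximation is poor there. With Fisher's exact test at the same looks, false benefit is 1.6–2.0% for the final analysis alone, 2.4–3.1% with two looks and 3.9–4.4% with four.

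**The case for a change.** The strongest case for a change is that the mismatch is real and cheap to remove. Efficacy is named first among the data the DMC reviews regularly, yet 11.5 does not mention it. Section 7.1 and the synopsis introduce their triggers as examples, so the list there is not closed. The power to advise on design is not limited to safety, and the sponsor holds the final decision. Calling efficacy exploratory does not settle the matter, because efficacy is among the primary objectives and has a named endpoint and test. A few sentences would cost no subjects and no power.

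Much of this stands as description: the remit is worded differently in different sections, and no legible line rules out acting on favourable efficacy. What does not stand is the step from there to a doubtful final test. An unstated prohibition is not a plan to stop for benefit. The natural homes for such a statement are the charter, which was not supplied, and the statistical text, parts of which are redacted, so its absence from the plan cannot be shown. The suggested sentences would mostly record what the plan already implies, and the final analysis would be the same with or without them.

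**Conclusion.** No change is needed. Sections 7.1, 9.5 and 11.5 can be read together without contradiction: the DMC sees efficacy for context, its stated actions rest on safety, and efficacy is tested once, at the end. The uneven description of the remit is a gap in wording that the charter and the analysts can fill sensibly.

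On that reading the false-benefit rate stays at 2.4–2.9%, given an assumed two-sided 0.05 and responder rates of 50–80%. The rise to 4.3–4.7% with two looks, or 6.5–7.8% with four, describes a different trial from the one written. The stakes are also modest, because this is a Phase 2 screening study of 80 subjects whose efficacy analyses are called exploratory.

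The conclusion rests on the legible text. It would need to be revisited if the charter or the redacted passages allowed stopping or redesign on favourable efficacy without a boundary.
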